10.2 Vital Signs and Weight

Weight and vital signs (including systolic blood pressure, diastolic blood pressure, pulse rate, respiratory rate, and body temperature) will be summarized for each treatment group. A comprehensive statistical description (number of subjects, mean, standard deviation, median, minimum, and maximum) of each parameter at baseline will be provided along with the change from baseline at each subsequent visit for subjects in the SAS. A subject-level listing will be provided.

10.3 Clinical Laboratory Evaluations

All chemistry, hematology and urinalysis results from the central laboratory will be comprehensively summarized into shift tables as normal, non-clinically significant abnormal, and clinically significant abnormal. Assessments of clinical significance for abnormal values were made by the investigator on results that were outside of the normal range. Comprehensive shift tables will compare the number and percent of assessments from each visit to baseline values for each treatment group.

All chemistry and hematology results from the central laboratory will be comprehensively summarized for each treatment group. Descriptive statistics of each laboratory test at all

timepoints will be provided along with the change from baseline at each subsequent timepoint for subjects in the SAS. The International System of Units (SI) will be used for all summaries.

Abnormal chemistry, hematology, urinalysis, and urine microscopy results for each subject will be provided in listings that will include laboratory test name, result, normal range, and an explanation for clinically significant values.

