14. Clinically significant abnormal screening hematology values, blood chemistry values, or urinalysis values as determined by the Investigator
15. Any condition, including laboratory findings not included in the Screening Visit 2 laboratory tests and findings in the medical history or in the pre-study assessments, that, in the opinion of the Investigator, constitutes a risk or contraindication for participation in the study or that could interfere with the study objectives, conduct, or evaluation
16. Comorbid conditions that could affect study endpoint assessments of the target knee, including, but not limited to, rheumatoid arthritis, psoriatic arthritis, systemic lupus erythematosus, gout or pseudogout, and fibromyalgia
17. Other conditions that, in the opinion of the Investigator, could affect study endpoint assessments of either knee, including, but not limited to, peripheral neuropathy (e.g., diabetic neuropathy), symptomatic hip osteoarthritis, symptomatic degenerative disc disease, and patellofemoral syndrome
18. History of mania, bipolar disorder, psychotic disorder, schizophrenia, schizoaffective disorder, major depressive disorder, or generalized anxiety disorder
19. Participation in a clinical research trial that included the receipt of an investigational product (IP) or any experimental therapeutic procedure within 26 weeks prior to Screening Visit 1, or planned participation in any such trial
20. Treatment of the target knee with intra-articular glucocorticoids (e.g., methylprednisolone) within 12 weeks prior to Screening Visit 1
21. Any intra-articular injection into the target knee with a therapeutic aim including, but not limited to, viscosupplementation (e.g., hyaluronic acid), platelet-rich plasma (PRP), and stem cell therapies within 24 weeks prior to Screening Visit 1; treatment of the target knee with intra-articular glucocorticoids greater than 12 weeks prior to Screening Visit 1 is allowed
22. Treatment with systemic (oral, intramuscular, or intravenous) glucocorticoids greater than 10 mg prednisone or the equivalent per day within 4 weeks prior to Screening Visit 1
23. Effusion of the target knee clinically requiring aspiration within 12 weeks prior to Screening Visit 1
24. Use of electrotherapy, acupuncture, and/or chiropractic treatments for knee OA within 4 weeks prior to Screening Visit 1 (refer to [Appendix 1](#))

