8 GENERAL ISSUES FOR STATISTICAL ANALYSIS

8.1 General Statistical Methodology

For continuous variables, the outcome measure at each visit, as well as the absolute change (outcome at visit – outcome at baseline), will be summarized within each treatment group using descriptive statistics (number of subjects, mean, standard deviation (SD), median, minimum, and maximum). The number of evaluable subjects in any analysis set may vary by endpoint/timepoint based on missing data. Categorical variables will be summarized with frequency tables.

All subject-level listings will be comprehensive and include subjects enrolled in both Phase A and Phase B. Data collected from unscheduled visits will not be included in summary tables but will be included in subject-level listings as appropriate.

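### The laboratory shift tables in SAP 10.3 do not show direction, and no planned table counts by arm the results that left the reference range on a given side

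*SAP*

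**What the plan says.** SAP 10.3 (Clinical Laboratory Evaluations) plans three displays.

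- **Shift tables** for chemistry, hematology and urinalysis, with results "comprehensively summarized into shift tables as normal, non-clinically significant abnormal, and clinically significant abnormal". The split between the two abnormal classes is the Investigator's: "Assessments of clinical significance for abnormal values were made by the investigator on results that were outside of the normal range". The layout is visit against baseline: "Comprehensive shift tables will compare the number and percent of assessments from each visit to baseline values for each treatment group". Neither this section nor any other divides abnormal results into low and high.
- **Descriptive statistics by arm** for two of the three panels: "All chemistry and hematology results from the central laboratory will be comprehensively summarized for each treatment group". These cover all "timepoints will be provided along with the change from baseline at each subsequent timepoint for subjects in the SAS". SAP 8.1 defines the change as a signed quantity: "absolute change (outcome at visit – outcome at baseline), will be summarized within each treatment group using descriptive statistics". Urinalysis is not included.
- **Listings** of abnormal chemistry, hematology, urinalysis and urine microscopy results, "provided in listings that will include laboratory test name, result, normal range, and an explanation for clinically significant values".

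Two protocol provisions also bear on the point. Exclusion criterion 14 in section 5.2 bars "Clinically significant abnormal screening hematology values, blood chemistry values, or urinalysis values as determined by the Investigator". Section 7.2.1 requires the Investigator to judge every out-of-range result, and to report as an AE any clinically significant abnormality found after injection.

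**The concern.** A laboratory shift table is meant to show, by arm, how many results moved out of range and to where. Here NCS stands for non-clinically significant abnormal and CS for clinically significant abnormal. With only normal, NCS and CS as classes, opposite findings are counted together. An alkaline phosphatase that goes from normal to above range and one that goes from normal to below range, both NCS, fall in the same cell. A corrected calcium that is below range at baseline and above range at Week 104, both NCS, falls on the diagonal and looks unchanged.

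When a treatment moves an analyte one way, results gained on one side are partly offset by results lost on the other. The pooled count then understates the one-sided change and can even move against it. Safety is the primary objective, and clinical laboratory measures belong to the general safety endpoint in both phases (SAP 3.1.1, 3.2.1, 3.2.5).

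**Working it through.** The plan states no figure on this point, so there is none to reproduce. The check has four parts.

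**1. What the table can and cannot separate.** Take five true states: CS-low, NCS-low, normal, NCS-high, CS-high. They give 5 × 5 = 25 transitions, which collapse into the planned 3 × 3 = 9 cells.

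- Eight of the nine cells pool low and high results; only normal-to-normal does not.
- There are 8 low-to-high or high-to-low transitions. Four keep the same significance class (NCS-low with NCS-high, CS-low with CS-high, each in both directions), so they lie on the diagonal and read as no shift. The other four change class and do appear as a shift, but without direction.
- If the baseline CS row is empty because of criterion 14, four of these transitions remain, and two lie on the diagonal.

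**2. Dilution in the pooled count.** Assumptions, not document figures: values are normal with SD 1, the reference limits are ±1.96 (2.5% beyond each side on placebo), and treatment shifts the mean up by s. Then high = P(Z > 1.96 − s) and low = P(Z < −1.96 − s).

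| s | High | Low | Pooled (placebo 5.0%) | Pooled ratio | High-only ratio (placebo 2.5%) |
|---|---|---|---|---|---|
| 0.3 | 4.8% | 1.2% | 6.0% | 1.2 | 1.9 |
| 0.5 | 7.2% | 0.7% | 7.9% | 1.6 | 2.9 |
| 0.8 | 12.3% | 0.3% | 12.6% | 2.5 | 4.9 |

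Off-centre case, also assumed: placebo has 5% low and 2% high, so the limits are −1.645 and 2.054. With s = 0.3, high = P(Z > 1.754) = 4.0% and low = P(Z < −1.945) = 2.6%. The pooled figure falls from 7.0% to 6.6% while high values double from 2.0% to 4.0%.

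**3. The same figures as subjects.** Take 50 per arm, the planned size (SAP section 6); numbers at later visits will be smaller.

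- At s = 0.5, high values are 50 × 0.072 = 3.6 subjects against 50 × 0.025 = 1.25. An observed 4/50 against 1/50 gives a Fisher p of 0.36.
- In the off-centre case, high values go from 1 subject to 2, and the pooled count from 3.5 to 3.3.

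**4. What the planned mean change already shows.** Let the within-subject correlation be r (assumed 0.5 to 0.7). The change has variance 2(1 − r), so the between-arm standard error is √(2 × 2(1 − r)/50). That is 0.20 at r = 0.5 and 0.155 at r = 0.7. A 0.5 SD shift is therefore 0.5/0.20 = 2.5 to 0.5/0.155 = 3.2 standard errors.

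A simulation used 50 per arm, r = 0.7 and true shifts of −0.8 and +0.8 SD, with 2000 runs. The normal-to-abnormal rates were 10.5% and 10.4%, so the shift table cannot tell the two apart. The mean changes were −0.80 and +0.80 SD, with the right sign in every run.

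**The case against.** The strongest reply is that the direction of an effect is reported elsewhere. For chemistry and hematology, the paragraph after the shift tables plans signed change from baseline by arm at every timepoint, and part 4 shows that this picks up a uniform shift far better than any count of tail values. The listings let a reader see which side of the range each abnormal result lies on. Clinically significant results after injection become AEs, which SAP 10.1 tabulates by preferred term and arm. The three classes also match the protocol summary, which assesses safety through changes that the Investigator judges clinically significant. All of this stands. A reader might infer from the shift tables that the plan hides the direction of any laboratory effect; the documents do not support that.

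Two further inferences fail.

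- That every low-to-high move counts as no shift: this holds only when the NCS/CS class is the same at both visits. Such moves are also very rare. Under the normal model with r of 0.5 to 0.7 and a shift of up to 0.8 SD, the chance is at most about 0.0001 per subject and analyte, or 0.005 subjects in 50.
- That the empty baseline CS row is a flaw: it follows from the eligibility rule, and the moves from normal or NCS to CS are still counted.

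What the reply does not supply is a count by arm of results above and below range. A mean can stay flat when a few subjects leave the range, or when individuals move in opposite directions. Minimum and maximum describe one subject each, and listings are not a comparison between arms. Urinalysis has no summary by arm other than the shift table, and two of its items, pH and specific gravity, are two-sided.

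**Conclusion.** The point holds as a minor reporting gap. The SAP 10.3 shift tables carry no direction, and no other planned table gives low and high out-of-range counts by arm. A one-sided rise can therefore be diluted in the pooled abnormal count (ratio 1.6 instead of 2.9 for a 0.5 SD shift) or, with off-centre limits, offset altogether. These sizes rest on assumed normal distributions and assumed reference-limit coverage. At about 50 per arm they amount to a few subjects, so the gain is in safety description and not in statistical power. No planned estimate is biased, and sample size and error rates are untouched.

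**What to change.** In SAP 10.3, use low / normal / high as the shift categories for all two-sided numeric tests: chemistry, hematology, and urine pH and specific gravity. Show the Investigator's NCS/CS flag within the post-baseline low and high columns, so that nothing in the present classification is lost. Keep the three existing categories for the remaining urinalysis items.

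The results, normal ranges and significance assessments are already planned for the SAP 10.3 displays, so the cost is reprogramming one set of tables. The only downside is that the tables become slightly larger.

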11 BONE IMAGING ANALYSIS

Whereas Phase A analysis (defined prior to unblinding) was the primary analysis for this study, data collected during Phase B complements the primary analysis by offering insight into safety after more than one year of treatment. Bone imaging analysis will be performed on the SAS.

A statistical description of target knee, non-target knee, spine, and hip BMD at baseline will be provided along with absolute and percent changes from baseline at each subsequent timepoint. Statistical descriptions of knee BMD for subgroups such as KL grade, sex, and age group may be provided.

Difference between target knee and non-target knee BMD will be summarized at baseline along with absolute changes from baseline at each subsequent timepoint. Spine and Hip BMD T-scores will be summarized at baseline only for subjects enrolled in Phase B.

Baseline-adjusted ANCOVA as described in [Section 8.1.2](#) will be used to analyze the change from baseline in BMD in the target knee and evaluated at Weeks 12, 24, 36, 52 (EOSa), 64, 76, 88, and 104 (EOSb).

Baseline-adjusted ANCOVA will also be used to analyze the within-subject difference in BMD between the target and non-target knee by qCT for SM04690, within-subject difference in BMD between the target and non-target knee by qCT for placebo, and change from baseline in BMD of the spine and hips by DXA for SM04690 subjects versus placebo. The models will be evaluated at Weeks 12, 24, 36, 52 (EOSa), 64, 76, 88, and 104 (EOSb) for qCT and Weeks 24, 52, 76, and 104 (EOSb) for DXA.

Knee BMD analysis will include all compartments and volumes of interest. Spine BMD analysis will include the adjusted total region of interest; hip BMD analysis will include both total hip and femoral neck regions of interest.

Subject-level listings will be provided.

12 EFFICACY ANALYSIS

A statistical description of Pain NRS at baseline will be provided along with absolute changes from baseline at each subsequent timepoint for subjects in the FASB and PPASB. Statistical descriptions of WOMAC Pain, WOMAC Function, Patient Global Assessment, and mJSW at baseline will also be provided along with absolute changes from baseline at each subsequent timepoint for subjects in the FASB only.

Changes in the target knee from baseline in Pain NRS will be characterized using MMRM for subjects in the FASB and PPASB; the models will be evaluated through Week 104 (EOSb). All models will use treatment group, week, treatment×week interaction, and baseline values as covariates. Unadjusted 95% confidence intervals and P values will be reported.

If a subject submitted data related to their non-target knee due to an electronic device error, this data will not be analyzed.

Subject-level listings will be provided.

Since Phase A analysis (defined prior to unblinding) was the primary analysis for this study, there will be no estimands provided for Phase B.

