10.4.3 ANALYSIS OF PHASE A EFFICACY AND EXPLORATORY BIOMARKER ENDPOINTS

Changes in the target knee from baseline in Pain NRS, WOMAC Function, WOMAC Pain, mJSW, and Patient Global Assessment will be characterized using MMRM; the models will be evaluated through Week 52. All models will use treatment group, week, treatment×week

interaction, and baseline values as covariates. Unadjusted 95% confidence intervals and P values will be reported.

For WOMAC, mJSW, and Patient Global Assessment, the model will be estimated assuming an unstructured variance-covariance matrix. For Pain NRS, the model will be estimated assuming a Toeplitz variance-covariance matrix. The Toeplitz structure is a more generalized form of autoregressive-1 structure, allowing the data to inform how the correlation between within-subject observations decreases over time instead of implicitly defining a uniform decay structure (Kincaid 2005).

To assess response durability, changes in the target knee from Week 24 (i.e., after second injection) in Pain NRS, WOMAC Function, WOMAC Pain, mJSW, and Patient Global Assessment will be characterized using MMRM; the models will be evaluated through Week 52. All models will use treatment group, week, treatment×week interaction, and Week 24 values as covariates. Unadjusted 95% confidence intervals and P values will be reported.

Baseline-adjusted ANCOVA will be used to analyze the change from baseline in serum bone biomarkers (e.g. PINP and β -CTX) and a serum cartilage biomarker (e.g., COMP) for SM04690 subjects versus placebo. The models will be adjusted for baseline and evaluated at Weeks 4, 12, 24, 36, and 52. Unadjusted 95% confidence intervals and P values will be reported.

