10.4.4 ANALYSIS OF PHASE B ENDPOINTS

Phase B endpoints will be analyzed in a similar fashion as Phase A endpoints. A separate SAP will be prepared for Phase B analyses.

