8.1.2 Analysis of Covariance (ANCOVA)

ANCOVA models will be used to analyze change over time in bone imaging endpoints. All models will be adjusted for baseline. Least squares estimates, two-sided 95% confidence intervals (unadjusted for multiplicity), and effect sizes will be provided.

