8.1.3 Mixed-Effects Models for Repeated Measures

A mixed-effects model for repeated measures (MMRM) will be used to analyze change over time in Pain NRS. The model will be estimated assuming a Toeplitz variance-covariance matrix. The Toeplitz structure is a more generalized form of autoregressive-1 (AR1) structure, allowing the data to inform how the correlation between within-subject observations decreases over time instead of implicitly defining a uniform decay structure (Kincaid, 2005).

MMRM presumes that missing data are not caused by something observable within the conduct of the trial (i.e. missing-at-random [MAR]). It is plausible to presume a MAR mechanism as there have been no observed tolerability issues to the administration of study injection during the prior development trials. Additionally, the study injection cannot be removed after it has been administered, eliminating study drug discontinuation as a source of treatment estimate confounding.

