15 CHANGES TO PLANNED ANALYSIS

For the Phase B exploratory biomarker endpoint, all changes were calculated from baseline instead of from Week 52.

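### The Phase B SAP fits a between-arm model only to Pain NRS, leaves the other four efficacy measures descriptive, drops the durability models, and does not list this among its changes

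*SAP*

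**What the plan says.** For Phase A, Protocol 10.4.3 states: "Changes in the target knee from baseline in Pain NRS, WOMAC Function, WOMAC Pain, mJSW, and Patient Global Assessment will be characterized using MMRM". The covariates are treatment group, week, their interaction and baseline, and unadjusted 95% confidence intervals and P values are to be reported. On covariance it says: "For WOMAC, mJSW, and Patient Global Assessment, the model will be estimated assuming an unstructured variance-covariance matrix". Pain NRS gets a Toeplitz matrix. The section then adds a second family of models, which also covers Patient Global Assessment: "To assess response durability, changes in the target knee from Week 24 (i.e., after second injection) in Pain NRS, WOMAC Function, WOMAC Pain, mJSW".

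For Phase B, Protocol 10.4.4 says "Phase B endpoints will be analyzed in a similar fashion as Phase A endpoints" and refers the reader to a separate SAP. SAP 5.2 repeats that sentence. SAP 3.2.7 lists ten Phase B efficacy endpoints: five on change from baseline and five on durability between injections.

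The SAP's methods are narrower. Section 8.1.3 says "A mixed-effects model for repeated measures (MMRM) will be used to analyze change over time in Pain NRS" and names no other measure. Section 8.1.2 says "ANCOVA models will be used to analyze change over time in bone imaging endpoints", and Section 13 extends ANCOVA to the biomarkers. Section 12 fits MMRM to Pain NRS in the FASB and PPASB. The other four measures are described at baseline and as absolute change at each timepoint, "for subjects in the FASB only". Those last words restrict the analysis set. The absence of a model follows from the rest of Section 12, where only Pain NRS is modelled.

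Section 15 declares one change: "For the Phase B exploratory biomarker endpoint, all changes were calculated from baseline instead of from Week 52".

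**The concern.** Effectiveness from Week 52 through Week 104 is part of secondary objective 3 in both documents. If the SAP is followed as written, the Phase B report will contain a planned, baseline-adjusted arm comparison for Pain NRS and none for function, WOMAC pain, global assessment or joint space width. The exploratory biomarkers, by contrast, do receive a baseline-adjusted ANCOVA, so listed efficacy endpoints are analysed less fully than exploratory ones.

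The second issue is disclosure. The SAP contains a section for departures from the planned analysis, and a reader of that section would conclude that the efficacy analysis is unchanged. The SAP's own Section 5.2 reinforces that impression.

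**Working it through.** No figure in the plan is in dispute here. The check sets the sections side by side, counts what is delivered, and asks whether the protocol's model can be fitted over the longer schedule.

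**Step 1. Planned and delivered, by measure.**

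| Measure | Protocol 10.4.3 (Phase A) | SAP Sections 8.1.3 and 12 (Phase B) |
|---|---|---|
| Pain NRS | MMRM from baseline, Toeplitz; durability MMRM | MMRM from baseline, Toeplitz; no durability model |
| WOMAC Pain | MMRM from baseline, unstructured; durability MMRM | Descriptive |
| WOMAC Function | MMRM from baseline, unstructured; durability MMRM | Descriptive |
| Patient Global Assessment | MMRM from baseline, unstructured; durability MMRM | Descriptive |
| mJSW | MMRM from baseline, unstructured; durability MMRM | Descriptive |

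**Step 2. Count.** One of five measures has a between-arm model, and 5 − 1 = 4 have none. Of the ten endpoints in SAP 3.2.7, endpoint 1 has its model. Endpoints 3, 5, 7 and 9 (change from baseline in the other four measures) have no model. Endpoints 2, 4, 6, 8 and 10 (durability) have no dedicated model. Endpoint 2 is a partial exception: the Pain NRS model carries treatment-by-week terms for every week to Week 104, so arm contrasts within each injection interval can be read from it, although they are not referenced to the re-injection visit.

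**Step 3. Other routes to an arm comparison.** ANCOVA in Sections 8.1.2, 11 and 13 covers bone imaging and biomarkers only. SAP 8.1 summarises each continuous outcome within treatment group (n, mean, SD, median, range). No other section supplies a between-arm estimate for the four measures.

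**Step 4. Declaration.** Section 15 holds one item, on the biomarker reference point. Section 12 adds that no estimands are given for Phase B because Phase A was the primary analysis. That does not say models were removed, and Pain NRS is modelled in the same section.

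**Step 5. Can the protocol's model be fitted?** An unstructured matrix over p post-baseline visits has p(p + 1)/2 parameters.

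- Monthly WOMAC and Patient Global to Week 104: p = 104/4 = 26, so 26 × 27/2 = 351 parameters. The trial randomised about 100 subjects, and the FASB cannot be larger. In Phase A the same structure had p = 52/4 = 13 and 13 × 14/2 = 91 parameters.
- mJSW at Weeks 24, 52, 76 and 104: p = 4, so 4 × 5/2 = 10 parameters.
- Toeplitz over 26 equally spaced visits: one variance and 25 lag covariances, so 26 parameters.

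The unstructured matrix is therefore impractical for the monthly measures in Phase B, but a repeated-measures model is not. For mJSW the protocol's structure can be kept. It also suits the uneven gaps there (28, 24 and 28 weeks).

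**The case against.** The best defence is that the Phase B commitment is only by reference. The MMRM text in Protocol 10.4.3 is written for Phase A and runs to Week 52. Protocol 10.1 says the section describes analyses in general terms, and 10.4.4 leaves Phase B to its own SAP. This stands, and it gives the SAP latitude over details such as covariance structure or visits. It does not stretch to dropping the treatment model for four of five measures and every durability model while SAP 5.2 repeats the commitment.

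A second defence is that Phase B is supportive. Protocol 10.2 plans no formal hypothesis test, Phase A is the primary analysis, and the efficacy endpoints speak of characterising change without naming a placebo comparison. The FASB also requires a Phase B injection, so it is selected after randomisation and arm differences in it are not a clean randomised comparison. All of this limits the weight of the point. However, Phase A had no formal test either and was still given estimates and intervals, and the selection applies equally to the Pain NRS model that the SAP keeps. A reader could compute an unadjusted difference from the group n, mean and SD, but that is neither planned nor baseline-adjusted.

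Three stronger readings are tempting, and the documents do not support them.

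- *The models were cut selectively after the sponsor saw the Phase A results.* The SAP's text does post-date the Phase A unblinding, because Sections 4.3 and 5.1 report that analysis as completed. That does not date the decision. The Phase A SAP is not among the documents and may already have narrowed the models. No motive can be inferred.
- *Nine of the ten endpoints have no between-arm information.* Endpoint 2 is partly informed by the Pain NRS treatment-by-week terms, so the count needs that qualification.
- *Losing baseline adjustment costs a known amount of precision.* At a single visit, with baseline-to-follow-up correlation r and baseline SD equal to k times the follow-up SD, SE(adjusted)/SE(raw change) = √[(1 − r²)/(1 + k² − 2rk)]. With k = 1 this gives 0.81 at r = 0.3 and 0.87 at r = 0.5, so the adjusted SE is 19% and 13% smaller. At r = 0.9 it gives 0.975. With k = 0.5 it gives 0.98 at r = 0.3 and 1.00 at r = 0.5, so there is almost no gain. These values of r and k are assumptions. The documents state neither, and inclusion criterion 10 restricts baseline WOMAC scores, which makes k = 1 doubtful. No single figure can be claimed.

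**Conclusion.** The point holds as an inconsistency between SAP Section 12 and SAP 5.2, and between the SAP and Protocol 10.4.3 read through 10.4.4, with no entry in Section 15. Four of five efficacy measures have no planned arm difference or confidence interval for the effectiveness part of secondary objective 3, and no durability endpoint has a dedicated model. The conclusion assumes that handling Phase B similarly means at least keeping a between-arm model for each measure.

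Model size may explain part of the reduction, since 351 covariance parameters cannot sensibly be estimated from about 100 subjects. The SAP does not give that reason, and it would not explain mJSW, which needs 10. The consequence is moderate: the Phase A primary analysis is untouched and Phase B remains supportive. It is worth correcting because the data are already collected and the remedy is simple.

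**What to change.** 1. In SAP Section 12, fit a repeated-measures model with treatment, week, treatment-by-week and baseline to WOMAC Pain, WOMAC Function, Patient Global Assessment and mJSW in the FASB through Week 104. Report arm differences with 95% confidence intervals, labelled supportive and unadjusted for multiplicity. Extend Section 8.1.3 to match.
2. Use an unstructured matrix for mJSW. For the monthly measures, name a parsimonious structure in advance, such as the Toeplitz already specified for Pain NRS, and record in Section 15 that this departs from the protocol's unstructured choice.
3. Either specify durability models for Phase B, including the reference visit, or state in Section 15 that they are dropped and why. If the Pain NRS weekly contrasts are meant to serve endpoint 2, say so.
4. List in Section 15, with reasons, any other protocol analysis deliberately omitted, and reword SAP 5.2 so that it agrees with Section 12.

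The cost is SAP wording and additional model runs on collected data. The drawback is more unadjusted estimates, in a set selected after randomisation, which is why they should be labelled supportive. If the sponsor prefers to keep the four measures descriptive, items 3 and 4 are the minimum: they settle the disclosure problem but leave those measures without a planned arm comparison.
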